In a pilot randomized study, we will include 60 healthy pregnant women. We will allocate 30 women to start aBME from week 34+0 of pregnancy until delivery and compare them to 30 women who does not perform aBME. All women included in this study will receive standard care, and have an individual consultation with a breastfeeding trained midwife in week 33 of their pregnancy. The women allocated to the intervention group will besides breastfeeding consultancy, also be taught how to perform aBME and store breastmilk correctly during the midwife consultation. To detect any signs of uterine contractions or fetal influence a cardiotocography (CTG) will be performed in the intervention group before, during and after the first aBME. In total 40 minutes of CTG surveillance. If the CTG is unclear, it will be assessed by the obstetric doctor in charge of this study, [name] or a substitute. In case of pathological CTG, the women will be send to the obstetric emergency department for further assessment. If the CTG is normal the women in the intervention group can perform aBME 5 minutes from each breast two times per day from week 34 until birth, and collect and store any expressed milk. They will be provided with a schedule to register their aBME sessions (Please see attachment).

Participants will receive both written and oral information about the trial and the intervention group will in addition receive safe storage of MOM (please see attachment 1, 2) and be provided with the needed syringes and labels for expressed milk. Participants will be instructed to be aware of precautions

related to aBME such as: continuous excessive painful contractions, vaginal bleeding or decreased fetal movements. In case of such symptoms they have to contact obstetric emergency department. During the intervention and 8 weeks after birth the participating women will receive weekly push-messages through an application on their smartphone. The messages include short questions about the aBME as well as regarding feeding of the infant after birth. At the end of the study we want to evaluate the mothers experience with the study through an online questionnaire. The questionnaire will be submitted as a supplement to this protocol when finished. All data is managed through OPEN/REDCap and stored in a secure server ([OPEN - Open Patient data Explorative Network - forside \(rsyd.dk\)](http://OPEN - Open Patient data Explorative Network - forside (rsyd.dk)))

Trial design

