
• Age• Smoking• Medications• Prepregnancy BMI• Delivery mode	
• Gestational age at birth• Gender• Anthropometry at birth• APGAR scores at 1 and 5 min• Umbilical cord pH• Feeding mode if hospitalized

Figure 1: Overall study design

Time	28-32 weeks of pregnancy	33 weeks	34 weeks	36 weeks	37 weeks	Admission for birth	8 weeks post partum
ENROLLMENT							
Eligibility for study screen	✗						
Informed content and information on email	✗						
Randomization to either active aBME or no aBME	✗						
INTERVENTION							
Group A: Midwife consultation		✗					
Group A: aBME 10 min a day intervention group A			→				
Group B: Midwife consultation		✗					
Group B: no aBME			→				
DATA COLLECTION							
Demographic maternal data	✗						
							✗

Obstetric data from medical records								Figure 2:
Neonatal data from medical records	Enrollment	Post randomization (intervention?)			Post-partum			Detailed
aBME data, and infant feeding data (App-tracking)								schedule
Mother's experience with the intervention (questionnaire)								of

participant enrolment, intervention and data assessment

Figure 3: Gantt diagram of project main time schedule

Event	Time	2021		2022			2023			2024		
Protocol writing and approval												
Ethical approval												
Training of staff and recruitment video production												
Patient recruitment and randomization												
August. 2022 – August. 2023												
Intervention												
August 2022 – August. 2023												
Data collection and outcome analyze												
Article writing												
Publication												

Outcomes:

Primary outcome:

1. Gestational age at birth comparing the two groups

Secondary outcomes

1. number of weekly antenatal stimulations/expressions (aBME) before birth
2. number of women in intervention group capable of expressing any milk
3. breastfeeding rates 1, 2, 4, 6 and 8 weeks after birth comparing the two groups
4. number of exclusively breastfeeding versus partial breastfeeding in each group at 1, 2, 4, 6 and 8 weeks after birth

5. Contractions and/or fetal stimulation during aBME, assessed with CTG
6. Women's experience with the intervention (separate qualitative study)

Sample Size

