In general the evidence in aBME is limited. A few prospective studies has been conducted, and only one larger RCT. This RCT included 635 participants, where aBME was performed from week 36 of pregnancy. They were not able to detect any difference in gestational age at birth or report any adverse events in relation to the aBME. Before the larger RCT they conducted a pilot study, which consisted of 43 participants. Our aim with this study is to primarily test safety and feasibility with the procedure aBME from week 34, and since no study has been done from this week of pregnancy, a reliable power calculation is not possible to make. Therefore we estimated that 30 participants in each group is a realistic and feasible number to include in the pilot study. To detect a difference in gestational age at birth based on 80% power, we estimated that we would need a total of 176 participants, 88 in each group (mean, SD, derived from Soltani et al(19)). If the pilot study shows no trend towards a higher proportion of preterm birth in the intervention group, we will proceed to the larger trial.

Data collection:

Demographic data on the mothers (maternal age, education level, ethnic background, parity and smoking status) will be obtained through medical files. Infant data on gestational age, complications such as preterm contractions or birth and feedings from birth, will be obtained from medical records after birth. To obtain data on aBME and breastfeeding rates after birth, we will use SMS tracking via an app based in the RedCap system. From intervention start until 8 weeks after birth participants in the intervention group will receive a weekly sms, with questions on how many times they stimulated and if they were capable of expressing any milk. The control group will receive a weekly message which regards if they have been giving birth, to be able to initiate the questions on breastfeeding. After birth questions will regard breastfeeding initiation. After eight weeks the mothers experience and evaluation on the study will be evaluated in an online questionnaire.

Data analysis and statistics:

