### 2.2 Adherence to the intervention

We consider all participants who answer weekly questionnaires until 8 weeks post-partum as full completers. E.g. if participants try to follow the intervention as well as possible, but do not stimulate the breast the recommended fourteen times a week, we will still consider them as completers of the study, if they have stayed in the study during the intervention and until eight weeks after birth. However, we will differentiate between study completion and intervention completion. Intervention completion is defined as participants who follow the intervention as well as possible until birth but do not answer all eight questionnaires. These participants will be included in the analysis for gestational age at birth, but will only be included in the breastfeeding analysis as long as they have answered the weekly questions. If participants do not want to perform stimulation anymore, we consider this as a withdrawal of consent. If participants are not adherent to the randomized group, e.g. they start to stimulate antenatal even though they are in the control group, we consider them as excluded from the study.

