#### Breastfeeding consultation

- Received other breastfeeding counseling (yes/no)
- Breastfed as a child (yes/partially/no)
- Partner participating in breastfeeding consultation (yes/no)

Only intervention group:

- CTG before stimulation (normal, deviant, or pathological)
- CTG under stimulation (normal, deviant, or pathological)
- CTG after stimulation (normal, deviant, or pathological)

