#### Antenatal breastmilk expression (weekly questionnaires)

- Did you perform abME this week (yes/no)
- If yes, how many times (amount of stimulations pr. week)
- Did you collect any milk (yes/no)
- If yes, how many milliliters (mL milk)

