## 4.2 Outcome measurement

### 4.2.1 Primary outcome

Safety: the primary outcome is gestational age at birth in the two groups. Median and interquartile range will be used due to the non-normality of this variable and non-parametric test (Ranksum test), to detect differences between groups.

A posterior plot for the probability of non-inferiority will be produced by Bayesian binomial regression with symmetric weakly informative priors.

Adverse events will only be reported for the intervention group as numbers and percentages: Bleeding, regular contractions, uterus pain, Braxton Hicks contractions, or others that will cover anything else. Self-reported by the women in the intervention group.

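### SAP 4.2.1 reports maternal adverse events in the intervention arm only, so any excess of symptoms during home expression cannot be told from the late-pregnancy background

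*SAP*

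**What the plan says.** The safety part of SAP 4.2.1 states: "Adverse events will only be reported for the intervention group as numbers and percentages". The events are bleeding, regular contractions, uterine pain, Braxton Hicks contractions and an open category, with the intervention-arm women's own report as the source.

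Three other places bear on the same symptoms:

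- **CTG.** The protocol (Intervention) says that "a cardiotocography (CTG) will be performed in the intervention group before, during and after the first aBME". It is a secondary outcome, "Contractions and/or fetal stimulation during aBME, assessed with CTG", and the SAP lists it under Breastfeeding consultation for the intervention group only, for example "CTG under stimulation (normal, deviant, or pathological".
- **Weekly messages.** Before birth the intervention arm receives a weekly text "with questions on how many times they stimulated and if they were capable of expressing any milk" (Protocol, Data collection). The SAP's weekly items match this, for example "If yes, how many times (amount of stimulations pr. week". For the other arm: "The control group will receive a weekly message which regards if they have been giving birth".
- **Medical records.** Protocol, Data collection, also takes complications, with preterm contractions as an example, from the records after birth. It sets no arm restriction. The SAP plans no analysis of them.

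**The concern.** The protocol's objective is to learn whether expression from week 34 is safe and feasible for mother and fetus. The listed symptoms can also occur late in pregnancy in women who do not express. A percentage from one arm mixes that background with any effect of the procedure.

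The error can go either way: ordinary symptoms may be blamed on expression, or a real excess may be dismissed as normal. The trial has a concurrent randomised control group that could supply the reference rate, but the SAP does not use it.

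The protocol's Interruption section names contractions and vaginal bleeding among the grounds on which investigators may stop the trial. Those two have no planned control rate. Its third ground, an excess of preterm birth, does have control data.

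**Working it through.** **Plan's own figure.** There is none on this point. The 176 participants (88 per arm) in the Sample Size section concern gestational age and have no bearing here.

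**Does another source fill the gap?**

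1. *CTG.* It is recorded at one session, in the intervention arm. SAP 2.2 gives the planned intensity when it speaks of women who "do not stimulate the breast the recommended fourteen times a week". From 34+0 to an assumed birth at 37+0 that is 14 × 3 = 42 sessions. To an assumed 40+0 it is 14 × 6 = 84. The monitored session is 1/42 = 2.4% or 1/84 = 1.2% of those planned. It gives a within-woman view of acute effects at that session and nothing on the weeks at home.
2. *Records.* They are collected without arm restriction, but no by-arm analysis is planned. Bleeding and uterine pain are not named there.
3. *Gestational age.* It is compared between arms, but does not capture contractions or bleeding that do not bring birth forward.
4. *Weekly items.* Those described cover stimulation and milk for the intervention arm and whether birth has occurred for the control arm. No symptom item is shown for either.

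**What the missing arm costs.** Inputs: 30 women per arm (Protocol, Participants/Population) and a 5% level (SAP 2.1), taken as two-sided. All symptom rates below are assumed.

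*One arm, as planned.* 15/30 = 50%, exact (Clopper-Pearson) 95% CI 31.3% to 68.7%. The excess over control is unknown.

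*Two arms.* Newcombe interval for the difference d = p1 - p2, with Wilson limits (l, u) for each arm:

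- lower = d - √[(p1 - l1)² + (u2 - p2)²]
- upper = d + √[(u1 - p1)² + (p2 - l2)²]

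The Wilson limits are 0.332 to 0.668 for 15/30, 0.035 to 0.256 for 3/30, and 0.006 to 0.167 for 1/30.

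| Intervention | Control | Difference | 95% CI |
|---|---|---|---|
| 15/30 | 15/30 | 0 points | -24 to +24 |
| 15/30 | 3/30 | +40 points | +17 to +58 |
| 1/30 | 1/30 | 0 points | -14 to +14 |

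The first two rows give an identical entry in the table that the SAP plans.

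*What a comparison could detect.* For 80% power, solve for the intervention-arm rate p1 at which (p1 - p2 - 1.96·√[2p̄(1 - p̄)/30]) / √[(p1(1 - p1) + p2(1 - p2))/30] = 0.84, where p̄ is the mean of the two rates:

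| Control rate | Intervention rate, normal approximation | Intervention rate, Fisher's exact test |
|---|---|---|
| 5% | 32.8% | 35.5% |
| 10% | 40.9% | 44% |
| 50% | 83.5% | 86% |

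For a true 20-point excess over background rates of 10% to 50%, power is 34% to 49%.

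**The case against.** The strongest reply has five parts.

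- **The decisions that matter do not use these symptoms.** Gestational age is compared between arms, and progression depends on preterm birth. The stopping text is discretionary and sets no rate threshold. This stands and limits the point to supporting safety data.
- **Events that reached care are probably in the records of both arms.** The protocol tells participants to contact the obstetric emergency department with painful contractions, bleeding or reduced fetal movements. For such events the data may exist and only the table is missing. That is largely right, but the SAP does not plan the table. Milder symptoms would still have no control rate.
- **The comparison would be imprecise.** It would, as the working shows. That is a reason to estimate with intervals and avoid claims. It does not justify having no comparator.
- **Unblinded self-report may exaggerate an excess.** Intervention-arm women are alerted to contractions and bleeding. Identical questions reduce this bias but do not remove it, so the record-based table is the sounder part of the remedy.
- **Symptom items may sit in material not shown.** The protocol mentions an end-of-study questionnaire still to be supplied and an attached registration schedule. The documents do not settle this. Even if such items exist, SAP 4.2.1 would still report only one arm.

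**Conclusion.** The concern holds. Followed exactly, SAP 4.2.1 yields uncontrolled percentages of non-specific symptoms, and nothing else in the plan supplies the reference rate for the weeks of home expression. On assumed rates, one planned result of 15/30 is consistent with no excess or with a 40-point excess.

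The loss is confined to supporting safety data, and the gestational-age comparison and the preterm-birth progression rule are untouched. The reading of the text rests on no assumption. The illustrative sizes rest on the assumed symptom rates, 30 women analysed per arm, and assumed birth at 37+0 to 40+0 for the session counts. This should be fixed but does not invalidate the trial.

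**What to change.** Amend SAP 4.2.1 as follows:

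1. Report adverse events by randomised arm, with risk differences and 95% CIs.
2. State the symptom questions and their timing, and put identical items in the weekly message that both arms receive before birth.
3. Tabulate by arm the complications already drawn from medical records, such as preterm contractions, including for women already delivered. Add bleeding if the records hold it.
4. Report CTG separately, labelled as first-session data from the intervention arm.
5. State that self-report is unblinded, and that with 30 per arm the intervals are too wide to support a conclusion of no harm.

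**Cost.** A few items must be written for an existing message and one two-arm table added, with slight extra burden for controls. SAP 3.5 says recruitment began on August 31, 2022, so self-report will be incomplete for controls already delivered. If data collection is far advanced, the record-based table carries the comparison and the self-reports should be labelled as uncontrolled.

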Data will be collected in order to meet the CONSORT guidelines for Randomized Controlled Trials. Comparability of the two groups by intention to treat analysis. Where data are normally distributed, comparison of means will be done using unpaired t-tests. If data are not normally distributed a non-parametric test for unpaired data will be used, eg. Mann-Whitney test or permutation test. Multivariate

analysis will be carried out, if data shows differences in maternal or infant characteristics possibly affecting outcome.

[Interruption of the trial](#)

The involved investigators can stop the trial if the protocol is not followed or unexpected adverse effects in relation to the aBME such as contractions, vaginal bleeding or overrepresentation of preterm birth in the intervention group. The investigators in charge can pull out participants if they find it irresponsible to continue due to side effects or new pregnancy related conditions, where aBME could be contraindicated. Participants can at any time retract their consent and stop the intervention.

[Patient insurance](#)

This trial is covered by the Patient Compensation Scheme and Labour Market Insurance.

[Publication](#)

All results, positive, negative as well as inconclusive results will be published.

[Possible clinical implication:](#)

We expect this initiative to have positive impact on both mother and infant with improved breastfeeding rates and mothers confidence with breastfeeding. If aBME from 34 weeks does not induce preterm birth, we aim to investigate if this procedure is safe earlier in pregnancy and especially among pregnant women at increased risk of preterm delivery. In the long term, this could increase the number of preterm infants fed exclusively MOM and possibly contribute to improved gut health and neurodevelopmental outcome for preterm infants.

Referencer

1. WHO/UNICEF. Global nutrition targets 2025: breastfeeding policy brief (WHO/NMH/NHD/14.7). Geneva: World Health Organization; 2014.

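### The SAP reports contractions only as self-reports in one group with no gestational window, and plans no analysis of the preterm contractions that the protocol takes from medical records

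*SAP*

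**What the plan says.** The protocol, under Data collection, states that "complications such as preterm contractions or birth and feedings from birth, will be obtained from medical records after birth". Preterm contractions are thus a named example of a complication, the source is the medical record, and neither group is left out.

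SAP 4.2.1 deals with adverse events differently. It says "Adverse events will only be reported for the intervention group as numbers and percentages". The categories are "Bleeding, regular contractions, uterus pain, Braxton Hicks contractions, or others that will cover anything else", and the source is "Self-reported by the women in the intervention group". It gives no gestational window and no rule for contractions that are simply the start of labour.

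Under the protocol's Intervention heading, women in the intervention group "start aBME from week 34+0 of pregnancy until delivery".

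The protocol's outcome list has one contraction outcome, "Contractions and/or fetal stimulation during aBME, assessed with CTG". It is separate from both the record item and the self-reports.

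**The concern.** The protocol's background names the safety worry: expression before birth might bring on preterm labour through oxytocin. Its first hypothesis is safety before week 36. A contraction count speaks to that worry mainly when it refers to preterm contractions and can be set against women who did not express.

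The figure planned in the SAP has neither property. It has no gestational limit and no comparator. The record-based item is preterm by its wording and could be compared between groups, but it has no planned analysis. A reader of the results would see a percentage of intervention women with contractions, pain or bleeding, and could not tell how much of it is normal late pregnancy.

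**Working it through.** The plan states no figure for this endpoint, so there is none to reproduce. The check is a comparison of the texts followed by simple arithmetic.

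**1. The two texts side by side**

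| Feature | Protocol, Data collection | SAP 4.2.1 |
|---|---|---|
| Event | preterm contractions, as an example of a complication | regular contractions, uterus pain, Braxton Hicks, bleeding, other |
| Source | medical records after birth | self-report |
| Group | no restriction stated | intervention only |
| Gestational limit | implied by the word preterm | none stated |
| Planned summary | none stated | numbers and percentages |

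**2. Is the record item picked up elsewhere in the SAP?** The lists in SAP 4.1 cover maternal data, the consultation (with CTG findings for the intervention group), weekly expression and infant data. None contains preterm contractions from records. SAP 4.2.2 covers breastfeeding and expression only.

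**3. Are the self-reports dated?** The weekly items in SAP 4.1 ask whether the woman expressed, how often, whether she collected milk and how much. The protocol's description of the weekly messages is similar. Neither has an adverse-event question, so when and how these events are reported is not stated.

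**4. How much of the window is at term?** Neither document defines preterm by week. I assume the usual cut at 37+0. For birth at week b, the share of the window from 34+0 to birth that lies at or after 37+0 is (b − 37)/(b − 34):

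- 38+0: 1/4 = 25%
- 39+0: 2/5 = 40%
- 40+0: 3/6 = 50%
- 41+0: 4/7 = 57%

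**5. What can be read from the SAP percentage?** This step is an illustration only, because the documents give no rates. Let p be the proportion of women with a preterm event and t the proportion reporting one at term or at labour onset, assumed independent. The unsplit proportion is 1 − (1 − p)(1 − t). With p = 0.20 (6 of 30 women):

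- t = 0.30: 1 − 0.80 × 0.70 = 0.44, or 13.2 of 30
- t = 0.50: 1 − 0.80 × 0.50 = 0.60, or 18.0 of 30
- t = 0.80: 1 − 0.80 × 0.20 = 0.84, or 25.2 of 30

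The same 60% also arises with p = 0.05 and t = 1 − 0.40/0.95 = 0.58. One unsplit figure therefore cannot separate a 5% from a 20% preterm proportion unless t is known.

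**The case against.** The best counter-argument is that these are two streams of data, not one variable that was redefined. The Data collection sentence gives an example and defines no endpoint, and preterm contractions are not in the protocol's outcome list. Elsewhere the protocol speaks of contractions without the preterm qualifier. Its Interruption section names "unexpected adverse effects in relation to the aBME such as contractions, vaginal bleeding or overrepresentation of preterm birth in the intervention group", and the SAP list fits that wording. This stands: a reader might infer two rival definitions of one endpoint, but the text does not go that far.

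A reader might also infer that the SAP counts contractions at every gestation and treats term labour as an adverse event. It says neither. It is silent, and the broad reading follows only from expression continuing until birth. The Interruption section's link to expression could narrow it, but SAP 4.2.1 does not carry that link over.

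A third tempting reading is that a preterm signal is hidden. The documents do not support it. Gestational age at birth is the primary outcome in both groups, and the decision to go on to the larger trial uses the proportion of preterm birth. No stated decision rule uses the adverse-event percentages.

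Finally, ratios of diluted to undiluted rates would describe a comparison that the SAP never makes, since the controls have no adverse-event data. That also stands.

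The objection does not explain why a relevant item that the protocol says will be collected has no planned analysis, or why the reported figure has no window.

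**Conclusion.** The concern holds in a limited form. The SAP as written yields a one-group percentage that can mix term and preterm events, and it leaves unanalysed a more relevant record-based item that could be compared between groups. What is blurred is a preterm-contraction signal, in particular contractions that do not end in preterm birth.

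The size cannot be stated. The window shares of 25% to 57% follow from the dates, given the assumed 37+0 cut. They show only how much time is open to term reports, not how many reports there will be. The proportions in step 5 rest on assumed rates and independence, and should not be read as the size of the problem. It is also unknown whether women would report labour onset as an adverse event at all.

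This is a cheap improvement to supporting safety data. It is not a flaw in the primary comparison.

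**What to change.** In SAP 4.2.1:

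- Add the number and percentage of women with preterm contractions (onset before 37+0) from medical records, in both groups, as a supporting safety result beside gestational age at birth. Count from the same starting week in each group. Keep contractions seen only on the study CTG apart, because only the intervention group has that recording.
- Move self-reported contractions, uterus pain and bleeding to a separate descriptive table for the intervention group, split at before 37+0 and from 37+0, with labour onset at term flagged on its own line.
- State how and when adverse events are self-reported, and record the gestational week of each report. The listed weekly items have no adverse-event question, so the split cannot be assumed to be available from them.

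The protocol already plans to obtain the record item, so that part costs SAP wording and one table. The self-report split may need a dated question. Where undated reports already exist, show them as such. With 30 women per group the cells will be small, so the tables should be read as description and not as tests.
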